#### 9.4 Safety Monitoring

Interim analyses of toxicity are performed twice yearly for all ECOG-ACRIN studies. Expedited reporting of certain adverse events is required through the CTEP-AERS system, which is monitored continuously with formal notifications monthly of unexpected grade 4 and 5 events. Formal comparison of toxicity rates between the arms is not a goal of this trial and the sample size will provide sufficient power for detecting only relative large difference in adverse events. With at least 69 patients per treatment arm, a 90% confidence interval on any adverse event rate will be no wider than 21 percentage points and there is at least 87% probability of observing one or more rare events (3% true probability) in either treatment arm.

Reports of these analyses are sent to the ECOG-ACRIN Principal Investigator or Senior Investigator at the participating institutions. Expedited reporting of certain adverse events is required, as described in Section [5](#).

## 9.5 Gender and Ethnicity

Based on previous data from the neuroendocrine stratum of ECOG study E4298 the anticipated accrual in subgroups defined by gender and race/ethnicity is as follows:

Ethnic Category	Gender		
	Females	Males	Total
Hispanic or Latino	3	3	6
Not Hispanic or Latino	69	70	139
Ethnic Category: Total of all subjects	72	73	145
Racial Category			
American Indian or Alaskan Native	0	0	0
Asian	0	0	0
Black or African American	3	3	6
Native Hawaiian or other Pacific Islander	0	0	0
White	69	70	139
Racial Category: Total of all subjects	72	73	145

The accrual targets in individual cells are not large enough for definitive subgroup analyses. Therefore, overall accrual to the study will not be extended to meet individual subgroup accrual targets.

Rev. 5/15

## 10. Imaging Studies

ECOG-ACRIN plan to bank CT images collected during the course of the study at the central ACR Imaging Core Laboratory. This data set of serial images from more than 130 patients with pancreatic NETs will serve as one of the largest NET image banks. For the ECOG-ACRIN E2211 trial, we plan to evaluate specific clinical data elements to associate images with treatment milestones and use these images to retrospectively evaluate internal imaging consistency methodologies, such as quality of images received, reproducibility, and compliance. In the future, the de-identified image bank may be used for additional research, such as retrospective reviews of disease or software validation. Patient identifiers will never be included in future research and no patients will be named in publications related to future research.

### 10.1 Standard-of-Care Imaging Time Points and Minimum Preferred Phases

Rev. 6/14

- 10.1.1 All standard-of-care imaging studies (including CT, MRI, PET, perfusion CT, or any combination) of the abdomen and pelvis, including all phases completed, will be submitted to ACRIN per Section [10.2](#) instructions. Submission of chest images is optional.
- 10.1.2 Standard practice imaging studies for the trial per E2211 procedures include:
  - Pre-treatment baseline scan for eligibility assessment;
  - Imaging studies during study-prescribed treatment—(e.g. CT scans or MRIs at the completion of cycles 3, 6, 9, and 12 (approximately every 12 weeks)).
  - Follow-up imaging studies—e.g. CT scans or MRIs approximately every 3 months for 3 years from randomization and 6 months for 3-5 years from randomization or until disease progression.
- 10.1.3 Preferably, a minimum of three (3) image phases will be submitted (see below), as well as any perfusion CT sequences that may be performed as standard institutional practice:
  - Preferred:
    - Late arterial phase through the abdomen;
    - Portal venous phase through the abdomen and pelvis;
    - Delayed (equilibrium) phase through the abdomen at 3 to 4 min after contrast administration;
  - If performed per standard institutional practice:
    - Perfusion CT sequences of an area of interest is optional and should be performed according to site specific specifications if available at the participating institution.

### 10.2 Images Submission

Rev. 7/15

- 10.2.1 For TRIAD Submission: The preferred image transfer method is via TRIAD, a software application that ACRIN provides for installation on a site's PC. One or several computers of choice within the institutional "firewall" and on the institutional network may be equipped with TRIAD software; Internet access is also required. The TRIAD

application can then be configured as a DICOM destination on either scanner(s) and/or PACS system for direct network transfer of study related images into the TRIAD directory. When properly configured, the TRIAD software anonymizes, encrypts, and performs a lossless compression of the images before they are transferred to the ACRIN image archive in Philadelphia. Once equipment-readiness has been determined, imaging personnel from ACRIN will coordinate installation and training for the software.

For more information, contact: [[contact]](mailto:[contact]) or call [contact].

- 10.2.2 For Submission Via Media: In the event that the transfer of image data is not available via TRIAD, images may also be sent on a CD/DVD-ROM to the ACRIN core lab for transfer to the image archive. All image data submitted to the ACRIN core lab must be in DICOM format.
- 10.2.3 The Imaging Transmittal Worksheet (ITW) must accompany all image submissions. PDF versions of the transmission worksheets, along with completion and submission instructions, are available on the ACRIN website.
- 10.2.4 Images may be mailed to:

American College of Radiology Imaging Network  
ACR Imaging Core Laboratory  
Attn: E2211  
[name]  
[name]

Rev. 6/14 11. Specimen Submission Requirements

Diagnostic material from previously collected tissue (core biopsy or surgical specimen preferred over FNA) must be submitted for central diagnostic review and classification and for laboratory research studies. These studies are defined in Section [12](#). Peripheral blood is to be submitted from consenting patients for future research studies.

All specimens submitted on this trial must be entered and tracked using the ECOG-ACRIN Sample Tracking System (see Section [11.3](#)). Any case reimbursements associated with specimen submissions to ECOG-ACRIN – designated laboratories will be determined only from data contained in STS.

Specimens are to be labeled clearly with the ECOG-ACRIN protocol number “E2211”, patient initials, date and time of collection, and sample type.

Rev. 5/15 11.1 Specimen Preparation Guidelines

11.1.1 Tissue Samples

Submission of pathology materials from all patients is **mandatory**. The submitting pathologist and clinical research associate should refer to [Appendix I](#) (Pathology Submission Guidelines) for guidelines and summary of submission requirements. Failure to submit the required materials for the central pathology review may render case unevaluable but will not impact patient participation in the trial.

The following materials are to be submitted within four (4) weeks following randomization:

- All original stained diagnostic slides.

**NOTE:** These slides will be returned to the site upon completion of the review which is retrospective and will be performed in batches. If the return of these slides is to be expedited:

1. Contact the repository to discuss expedited review. They may request that materials be held until requested.
2. Upon submission, indicate need for expedited review in the appropriate comment field in STS.
3. If submission is delayed, a copy of the pathology report must be submitted and it is requested that the delay or inability to submit the materials be indicated in STS.

- One representative diagnostic formalin-fixed paraffin-embedded **tumor block**, core biopsy or surgical specimen preferred.

**NOTE:** If a block is unavailable for submission, submit the following:

- Twenty (20) unstained slides 4 $\mu$ m thick
- Two (2) 4mm cores.

If these criteria cannot be met, please contact the ECOG-ACRIN Central Biorepository and Pathology Facility ([[contact]](mailto:[contact])) to obtain alternative submission requirements.

- Forms:
  - A copy of the surgical (if appropriate) and pathology reports and Immunologic studies (if available). If tissue submissions are delayed, reports are still required to be submitted following registration.
  - Sample Tracking System Shipping Manifest

Rev. 6/14

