## 6. Measurement of Effect

### 6.1 Antitumor Effect – Solid Tumors

For the purposes of this study, patients should be re-evaluated for response every 12 weeks. In addition to a baseline scan, confirmatory scans should also be obtained 4 weeks following initial documentation of objective response.

Response and progression will be evaluated in this study using the international criteria proposed by the revised Response Evaluation Criteria in Solid Tumors (RECIST) guideline (version 1.1) [Eur J Ca 45:228-247, 2009]. Changes in the largest diameter (unidimensional measurement) of the tumor lesions and the shortest diameter in the case of malignant lymph nodes are used in RECIST.

The following general principles must be followed:

1. To assess objective response, it is necessary to estimate the overall tumor burden at baseline to which subsequent measurements will be compared. All baseline evaluations should be performed as closely as possible to the beginning of treatment and **never more than four weeks** before randomization.
2. Measurable disease is defined by the presence of at least one measurable lesion.
3. All measurements should be recorded in metric notation by use of a ruler or calipers.
4. The same method of assessment and the same technique must be used to characterize each identified lesion at baseline and during follow-up.

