#### 6.1.1 Definitions

##### Evaluable for Objective Response

Only those patients who have measurable disease present at baseline, have received at least one cycle of therapy, and have had their disease re-evaluated will be considered evaluable for response. These patients will have their response classified according to the definitions stated below.

**(NOTE:** Patients who exhibit objective disease progression prior to the end of cycle 1 will also be considered evaluable.)

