5. If only MRI of the abdomen and/or pelvis is available, this can be substituted for CT of abdomen and/or pelvis, but CT of chest should still be obtained. Copies of all standard-of-care imaging studies are to be submitted to the American College of Radiology Imaging Network (ACRIN) and the ACR Imaging Core Lab as outlined in Section [10](#).

6. Must be done within 2 weeks prior to randomization.

7. Post treatment scans will be performed every 3 months for 3 years from randomization and every 6 months between 3-5 years from randomization. The collection of tumor markers is encouraged at this time, but not required. Once there is confirmation of progression, scans and tumor measurements no longer have to be performed.

Rev. 6/14 8. Representative tumor tissue (block preferred) and related pathology reports are to be submitted for central diagnostic review and classification and defined research studies within 4 weeks following randomization as outlined in Section [11](#). Failure to submit the required materials may render the case unevaluable but will not impact patient participation in the trial.

9. Research blood sample may be collected at any time during the trial, although prior to start of treatment is preferred. EDTA may be used if ACD not available. Submit from patients who answer "Yes" to "I agree to provide additional blood for research" as outlined in Section [12](#).

Rev. 6/14 10. Imaging instructions: All standard-of-care imaging studies (including CT, MRI, PET, perfusion CT, or any combination) of the abdomen and pelvis will be submitted to ACRIN via the ACR Imaging Core Lab per Section [10.2](#) instructions. Submission of chest images is optional. Preferably, a minimum of three (3) image phases will be submitted (see below):

Preferred:

- Late arterial phase through the abdomen
- Portal venous phase through the abdomen and pelvis
- Delayed (equilibrium) phase through the abdomen at 3 to 4 min after contrast administration.

If performed per standard institutional practice:

- Perfusion CT sequences of an area of interest is optional and should be performed according to site specific specifications if available at the participating institution.

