### 9.3 Statistical Design and Efficacy Monitoring

The primary endpoint of this trial is progression-free survival (PFS). Patient assessments will be made every 3 months.

This study will require a minimum of 138 patients (or a maximum of 145 patients to allow for 5% ineligibility) to be accrued at the rate of roughly 6 patients per month. With 23 months of accrual time and 13 months of follow-up (3 years total study time), this trial will have at least 81% power to detect a difference in median PFS between the treatment arms of 9 versus 14 months (hazard ratio of 0.64) using a two-sided log-rank test at the overall 0.20 significance level. The assumption of 9 months for the temozolamide arm is based on historical data of temozolamide alone and temozolamide-based regimens as described in the introduction. The assumption of 14 months for the combination arm is based a goal of improving treatment by 55% (which conservatively approximates the Strosberg PFS data of 18 months).

There will be two log-rank tests conducted, an interim analysis at 76% information (at 80 PFS events, projected to occur just after the end of the accrual period at 26 months) and a final analysis at 100% information (105 PFS events), projected to occur at 3 years from the start of accrual. The overall type I error will be controlled using an O'Brien-Fleming boundary function. Using this boundary, if the repeated two-sided 95% confidence interval on the hazard ratio does not contain the target alternative hazard ratio of 0.64, consideration will be given to declaring the study negative and reporting the results. If the interim log-rank test is positive, the study can be reported early before the projected end of the follow-up period.

Response rate (RR) will be a secondary endpoint. RR will be defined by revised RECIST criteria version 1.1 and include complete responses and partial responses. Prior studies of single agent temozolomide suggest that the response rate associated with single-agent temozolomide is 8-24%; however, overall response rates associated with other temozolomide-based regimens in this disease are between 30-40%. For the purposes of this study, we assume that single agent temozolomide will be associated with a response rate of 33%. Retrospective series of temozolomide/capecitabine have reported response rates of 59-70% in advanced pancreatic neuroendocrine tumors.

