### 12.1 Pathology Review

The appropriate representative tumor tissue samples will be forwarded to [name] for central diagnostic review and classification to confirm the diagnosis of low or intermediate grade pNET. This is a retrospective review to determine the evaluability of the patient's data for data analysis. The results of the review are for the purpose of the trial only and will not be returned to the site.

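### Can a missing tissue submission, said to make a case possibly unevaluable, remove patients from the primary PFS comparison?

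*Combined protocol and SAP*

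**What the plan says.** Section 11.1.1 makes pathology submission mandatory within four weeks after randomisation and adds: "Failure to submit the required materials for the central pathology review may render case unevaluable but will not impact patient participation in the trial". Note 8 to the calendar in Section 7.1 repeats it: "Failure to submit the required materials may render the case unevaluable but will not impact patient participation in the trial". Section 12.1 describes the central review that uses the material: "This is a retrospective review to determine the evaluability of the patient's data for data analysis". None of the three names an analysis.

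Evaluability is defined only in Section 6.1.1, for objective response and for non-target disease. The response definition begins "Only those patients who have measurable disease present at baseline, have received at least one cycle of therapy" and goes on to require a re-evaluation of disease. Tissue is not a condition in either definition.

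Section 9.3 gives the primary endpoint (PFS), the log-rank test, 138 patients or "a maximum of 145 patients to allow for 5% ineligibility", an interim look at 80 events and "a final analysis at 100% information (105 PFS events"). It does not say in words which patients enter the PFS comparison.

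**The concern.** The trial is open-label, and under Section 4 the site receives the treatment assignment when it randomises. Sending tissue is therefore a site action taken with the arm known. Section 11.1.1 expects some shortfall, since "it is requested that the delay or inability to submit the materials be indicated in STS", and the review is retrospective and done in batches. If a missing block could take a patient out of the PFS analysis, and if that were related to arm and outcome, the protection given by randomisation would be weakened. In a trial of 145 patients tested at a two-sided 0.20 level, a handful of selective removals could matter. The 5% allowance in Section 9.3 is for ineligibility and leaves no room for further loss.

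**Working it through.** **The plan's own figures.** Assume uniform accrual over A months, exponential PFS with rate λ = ln 2 / median, and analysis at month T. The expected events in an arm of n patients are n × [1 − (e^(−λ(T−A)) − e^(−λT)) / (λA)].

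- Section 9.3 inputs: 69 per arm, A = 23, T = 36, medians 9 and 14 months.
- Arm A: 69 × [1 − (0.367 − 0.0625)/1.771] = 57.1.
- Arm B: 69 × [1 − (0.525 − 0.168)/1.139] = 47.4.
- The total is about 104.5, against the stated 105.
- Two-look power at hazard ratio 9/14 with an O'Brien-Fleming-type boundary at 80 and 105 events is 82.7%, against the stated minimum of 81%.
- 145 × 0.95 = 137.75, the planned 138. The 138 are therefore the eligible patients.

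**Does missing tissue make a patient ineligible?** Section 12.4 expects about 75% of cases to yield usable tissue and works with roughly 104 eligible patients who have samples. Since 0.75 × 138 = 103.5, that 104 is drawn from the full 138. The eligible count is not reduced for missing tissue. The 75% includes assay yield, so it is not a submission rate.

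**How free is the site to select?**

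- Section 11 asks for tissue already collected, and criterion 3.1.1 requires histological or pathological confirmation before entry. Whether tissue exists is thus settled before randomisation, and only the shipping comes after it.
- Section 11.1.1 accepts slides and cores where no block is available, then alternatives agreed with the repository. It requires the pathology report even when tissue is late.
- Section 11.2.1.1 gives four weeks, and Appendix I calls one month the deadline.
- Section 6.1 says "patients should be re-evaluated for response every 12 weeks". Selecting on the first scheduled scan therefore needs a submission already 12 − 4 = 8 weeks late.
- At a 9-month median, events by week 4 in an arm of 72 number 72 × (1 − e^(−(ln 2/9) × 28/30.44)) = 4.9.

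**Cost in time.** Solving the event formula for 105 events, with 145 patients entered at 6 per month (A = 24.17) and medians 9 and 14:

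| Removed | Patients left | Month of 105th event |
|---|---|---|
| 0% | 145 | 34.6 |
| 5% (as planned) | 137.75 | 37.1 |
| 10% | 130.5 | 40.4 |

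If the analysis did not wait and 10% of the 105 events were lost, two-look power would be 79.6%.

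**Bias.** The documents give no non-submission rate, so the removals below are assumptions. Each scenario used 20,000 simulated trials with no true difference (both medians 9 months), 72 against 73 patients and one unstratified log-rank test at month 36. The entry is the chance of z beyond 1.2816 in favour of one given arm. Early means progression before month 3.

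| Removed | False-positive rate |
|---|---|
| None | 10.0% |
| 3, 5 or 7 at random, one arm | 10.2%, 10.1%, 10.3% |
| 3, 5 or 7 early, each arm | 10.6%, 10.8%, 11.7% |
| 2 early and 5 random, one arm | 13.3% |
| 5 early in one arm, 2 early in the other | 16.3% |
| 3, 5 or 7 early, one arm only | 15.6%, 19.9%, about 25% |

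For scale, 72 × (1 − e^(−(ln 2/9) × 3)) = 14.9 early progressors are expected per arm. Removing 7 in one arm only means losing nearly half of them there and none in the other arm.

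The month-36 look does not match the plan. Under this null, 145 × [1 − (0.402 − 0.0625)/1.861] gives about 119 events by then, and 105 would be reached near month 31. The runs also leave out the interim look and stratification. They show direction and order of size only.

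**The case for a change.** The best case for acting is that the clause is discretionary. Whoever sets the analysis set could decide late, perhaps with outcomes in view, that an undelivered block disqualifies a patient. Section 12.1 speaks of data analysis in general, so the clause cannot be read with certainty as covering MGMT work only. Sections 4.7 and 5.6, which keep collecting follow-up on everyone, are data-collection rules and define no analysis population. The remedy would be a few words.

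Part of this stands. The term is undefined for this purpose, Section 9.3 leaves the PFS population to inference, and no text says when a late submission becomes a failed one. What does not stand is the step to a faulty plan. Section 12.1 says the review is to confirm low or intermediate grade disease, a baseline eligibility question of the kind the 5% allowance serves. The passages do not contradict each other, and no stated rule yields a wrong result. The larger error rates come from assumed site behaviour that the documents give no reason to expect.

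**Conclusion.** No change is called for. The protocol leaves a term undefined and a population unstated. The sensible reading is that PFS is compared by assigned arm among patients eligible on baseline criteria, and that a case without tissue is unevaluable for the pathology and MGMT work. That agrees with the 138 and the 104. Follow-up is collected on all patients, so nothing needed for that analysis, or for an all-randomised one, is lost.

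Under random or similar loss in the two arms, the one-sided false-positive rate stays at about 10% to 12% against a nominal 10%. Because the final analysis is set by events, further loss mainly costs time, about three months if 10% rather than 5% of patients are removed. The 13% to 25% figures need arm-specific withholding of tissue for early progressors and should not set the weight of this point. The conclusion assumes that the analysts do not treat missing tissue alone as a reason to drop a patient from PFS. The protocol does not tell them to do so.

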#### 11.1.2 Peripheral Blood, ACD or EDTA

Blood specimens are to be submitted for future research studies from patients who answered "yes" to "I agree to provide additional blood for research."

Samples are not to be drawn until after patient has been randomized to treatment. Although collection prior to start of protocol treatment is preferred, the sample may be drawn at any time during study participation.

- Draw blood into two 10mL ACD or EDTA tubes. Invert gently eight to ten times to thoroughly mix the blood and anti-coagulant.
- Specimen may be shipped at ambient temperature the day of collection or frozen (at < -70°C preferred). If frozen, specimens collected in glass vacutainers must be transferred to sterile cryovials prior to freezing. Plastic vacutainers may be frozen directly.

